#### 4. GOAL AND OBJECTIVES

We propose to maintain patient safety while reducing the substantial VMMC follow-up workload burden by using two-way mobile phone texts to provide in-person review only for men who indicate a desire or need for follow-up. This tailored approach to post-procedure VMMC care could reduce unnecessary visits and remove barriers for VMMC clients without deterioration of quality care. I-TECH's diverse, expert team of researchers from the University of Washington, Seattle, USA; Aurum Institute's office in Johannesburg; and Medic Mobile, Nairobi, Kenya, will test this mHealth intervention. We believe that bi-directional, interactive, text-based short message service (SMS) during the most critical 14 days after circumcision will help men identify and act on any sign of an adverse event, thereby seeking in-person follow-up only when an AE is suspected and reducing unnecessary visits. Reduced in-person follow-up could also free healthcare workers to perform additional **VMMC** surgeries. Using a prospective, randomized control trial (RCT), our intervention compares two groups of clients with cell phones: 1) standard care (control group) and 2) clients who receive and respond to a daily text with in-person follow-up only if desired or if an AE is suspected (intervention). Both arms complete a study-specific, Day 14, in-person, follow-up review for verification of self-reports (intervention) and comparison (control). Our specific objectives are to:

Objective 1: Determine if 2-way texting can safely reduce VMMC follow-up visits

Approach: Un-blinded, prospective, non-inferiority, RCT in high-volume facilities providing VMMC. Two-way texting (**2wT**) will provide interactive, text-based follow-up. 2wT men healing without complication could decline in-person follow-up; those with suspected AEs will be referred to in-person care. We will compare the safety outcome of combined moderate or severe AE rate ≤ Day 14 post-VMMC and the workload outcome of average number of in-person follow-up visits between control and intervention arms.

Objective 2: Estimate the cost savings associated with 2wT over routine VMMC follow-up

Approach: We will determine the programmatic costs of 2wT from a systems perspective, including the technology , healthcare worker costs, and client perspective (travel, text costs, missed work). We will estimate the incremental

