#### 5. Study Design

Study overview: Following usability testing with both healthcare workers and 2wT VMMC clients during a ~50-man pilot, we will test if two-way texting (2wT) reduces unnecessary follow-up visits without compromising patient safety (Objective 1) using a randomized control trial in large, urban VMMC clinics. We will assess the costs of 2wT from technology, healthcare worker, and client perspectives to determine the costs incurred by NDoH if adopted for scale-up (Objective 2). We will assess acceptability and feasibility working towards system integration and sustainability in RSA and beyond (Objective 3).

Objective 1: Technology overview: Studies that demonstrate the impacts of mHealth interventions too often have evaluated technologies that are made 'from scratch' and as a result are not robust enough to merit widespread replication 41,49.By partnering with a well-established non-profit mHealth organization. Medic Mobile (http://medicmobile.org/), and integrating with their existing software platform. open-source community and current efforts to integrate with existing health

Reply to [name]

Figure 2: Medic Mobile messaging inbox interface

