#### RANDOMIZATION PROCESS:

We will conduct randomization using a randomized block design, ensuring that each group of 20 envelopes has 10 intervention and 10 control per block, shuffling each block to ensure a near random order. The full set of 1104 will be numbered before distribution to sites. Each group assignment envelope will be selected by the coordinator and then opened by the participant and shown to the coordinator or 2WT enrollment coordinator. Security envelopes will be used to help prevent selection of assigned group. Subjects within each block are randomly assigned to treatment conditions. This design reduces variability within treatment conditions and potential confounding, allowing for more interim analysis with near equal size groups and more certain randomization within sites.

Standard VMMC care (Control arm): For the 552 men randomized into the control arm, Aurum Institute follows all NDOH protocols based on WHO guidelines  including routine surgical VMMC follow-up on post-surgery days 2, 7 and 21 (Table 1) . Patients may seek care outside scheduled visits for suspicion of AEs at any healthcare facility at any time but most often return to their VMMC site. Referral cards for VMMC clients provide local numbers for patients to text, call, or request a call back for emergencies. A standardized approach is used to assess, identify, and record the severity of AEs . All VMMC care, from assessment of all AEs through complete healing, is provided free to clients from NDoH. Clients who do not return to the clinic for follow-up on Day 2 or Day 7 are traced: 3 attempts by phone and then 1 attempt at in-person tracking after which they are considered lost to follow-up (LTFU). There is no tracing for Day 21 visits. For the purposes of this study, control arm VMMC clients will be asked to come in on Day 14 for an additional follow-up visit. Active follow-up by phone call is provided at Day 14.

[figure not shown]

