VMMC care procedures (2wT arm): We will conduct a prospective, un-blinded, randomized control trial (RCT) among VMMC clients in a 1:1 ratio of control to intervention. Study participants and clinic staff are not masked to treatment. For the 552 men randomized into the intervention arm, men in the 2wT will receive routine VMMC surgical care and counseling, including referral cards for emergencies. 2wT clients will receive automated daily texts from days 1-14 (Table 1 and Figure 3). It is free to receive call and texts; it costs approximately R0.20 to send a SMS in RSA . If they respond that they suspect no adverse event, no immediate follow-up action will be taken. If a 2wT VMMC client responds affirmatively to any daily text that he

[figure not shown]
suspects an AE, a VMMC nurse will exchange modifiable, scripted texts with the client to determine the symptoms, frequency, and severity. Then, if deemed necessary, the client will be asked to return to clinic the following day or earlier if an emergency is suspected. AE management will adhere to NDOH standard care. If 2wT patients do not respond to texts on Day 2 or Day 7, the same NDOH tracing process will be activated on Day 14, after which they will be considered LTFU. All study participants will be asked to come to the clinic for study-specific, Day 14 follow-up to review healing and verify adverse event reporting. Day 14 was chosen for verification because 95% of all AEs within a similar VMMC program in Zimbabwe are reported Day 14 or earlier 61, suggesting that most AEs have occurred by this time point. In a previous field study of AEs, the most common AEs of bleeding and infection were found a mean of 6.7 and 9.0 days, respectively, after VMMC , further supporting the 14 day period used in this and a previous study. The Day 14 review will be conducted by routine VMMC providers according to NDOH review guidelines. At Day 21, we will implement a brief text-based survey with 2wT clients to ascertain complete healing, providing stronger inferences at study completion.

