#### FUTURE PLANS:

If texting with VMMC clients is found to be superior to routine, in-person follow-up for detection of AEs, scale up could dramatically reduce time spent on unnecessary VMMC follow-up visits by healthcare personnel and decrease the burden on VMMC clients. Future funding could enable scale-up of the intervention in other high volume VMMC sites with high mobile phone coverage, conducting additional rigorous evaluation in diverse field and clinical contexts. We would seek funding to test 2wT among rural populations or smaller urban areas. Lastly, we will explore how 2wT could be integrated into DHIS2, or other national health information system, to improve and ease reporting.

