To test our noninferiority hypothesis, we will compare cumulative proportion (rate) of any moderate or severe AE ascertained \leq Day 14 between groups by comparing the lower limit of the one-sided 95% confidence interval of the difference in proportion between groups, to the noninferiority margin. The rates will be calculated per arm as: (# moderate + severe AEs)/(total # MC clients who attend 2, 7 or 14 Day follow-up visit). Based on our RCT in Zimbabwe, we may actually observe an increase in AEs; in that case, we will then seek to establish superiority of the two-way texting group by comparing arms with Fisher's exact test. While our study design provides limited power for this comparison (45%), there's no statistical impediment to performing both noninferiority and superiority comparisons in a noninferiority trial. To determine follow-up visit reduction, we will compare the mean number of in-person visits for intervention and control using a t-test. A multivariate linear regression model will further quantify the effect of intervention on visit reduction, adjusting for potential confounders. Secondary outcomes include: AE rates on Day 14, texting response rate, time between 2wT AE text reporting and follow-up, severity of AEs. We will perform appropriate summaries of missing data and LTFU, testing for systematic differences in response by study arm. We will examine individual mediating (e.g., referral follow-up, response rate) and moderating (urban/rural) variables ³. *We hypothesize that 1) 2wT is non-inferior to routine follow-up for patient safety and that 2) 2wT will reduce unnecessary follow-up over standard care.*

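### Text response rate cannot mediate the arm effect because control men receive no texts, and the urban/rural moderator depends on a trial setting that the protocol states in two ways

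*SAP*

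**What the plan says.** The SAP gives this analysis one sentence, near the end of data analysis item 1: "We will examine individual mediating (e.g., referral follow-up, response rate) and moderating (urban/rural) variables". It names no outcome, model, definition or method of measurement. The sentence carries SAP reference 3, a methods paper on the moderator–mediator distinction.

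The related statements are:

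- **Response.** The same SAP paragraph lists as secondary outcomes "texting response rate, time between 2wT AE text reporting and follow-up, severity of AEs". Just before the mediator sentence, in the context of missing data and loss to follow-up, it plans "testing for systematic differences in response by study arm".
- **Who is texted.** Protocol section 6 says "2wT clients will receive automated daily texts from days 1-14". In Table 2 the daily-text row is marked for 2wT and blank for control.
- **Referral.** Protocol section 4 says of the 2wT arm that "those with suspected AEs will be referred to in-person care". Of standard care (control), section 6 says "Patients may seek care outside scheduled visits for suspicion of AEs at any healthcare facility at any time". Both arms receive referral cards.
- **Setting.** Protocol section 5 describes "using a randomized control trial in large, urban VMMC clinics". Under Future Plans it adds "We would seek funding to test 2wT among rural populations or smaller urban areas". Table 2 gives both rural and urban as the location of the randomized phase (552 and 552 men). The recruitment-sites paragraph names two districts without classing their clinics.

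**The concern.** To split a between-arm effect into a part that passes through a mediator and a part that does not, the mediator must have a meaning and a value in each arm. Text response does not: a man who is sent no texts has no response rate. If the sentence is carried out in the way its reference suggests, the output would be a statement that some share of the effect on visits or AE detection is mediated by response. That could be read as evidence of how texting works, in a trial meant to inform national scale-up, although randomization does not support it.

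The moderator raises a separate question. Whether urban/rural varies at all depends on which statement of the setting is right. If it does vary, the AE outcome has very few events to support an interaction.

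**Working it through.** **1. Where a response coefficient would come from.** Let A = 1 for 2wT and 0 for control, and let R be a texting man's response rate. The mediator can be entered in both arms only as M = A × R, which is 0 for every control. Fit Y = b0 + b1·A + b2·M:

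- Controls have A = M = 0, so they determine b0 and nothing else.
- Among texting men Y = (b0 + b1) + b2·R, so b2 is the slope of outcome on response within that arm.
- The total effect is b1 + b2 × mean(R). The so-called direct effect b1 compares texting men extrapolated to zero response with the whole control group.

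Response is not randomized, and men who do not reply may differ in healing, phone access or care-seeking. The split therefore rests on assumptions that the trial cannot test, whatever its size.

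**2. Expected events.** First the SAP's own sample size (0.5% v 2.0%, margin 0.25 points, one-sided 5%, 80% power):

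n = (1.645 + 0.842)² × (0.005×0.995 + 0.02×0.98) / (0.015 + 0.0025)² = 6.183 × 0.024575 / 0.00030625 ≈ 496.1, so 497 per arm and 994 in total. 994/0.9 = 1104.4. The stated 497, 994 and 1104 are reproduced.

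Expected AEs: control 497 × 0.005 = 2.5; 2wT 497 × 0.02 = 9.9; total 12.4.

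**3. Information on non-response.** The documents give no expected response proportion, so a range is assumed. Score any response as 1 or 0 in 2wT and 0 in control. With responding proportion p, the correlation with arm is √(p/(2−p)). Expected AEs among non-responders assume 2% regardless of response.

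| p (assumed) | correlation with arm | non-responders, 497(1−p) | expected AEs among them |
|---|---|---|---|
| 0.80 | 0.82 | 99 | 2.0 |
| 0.90 | 0.90 | 50 | 1.0 |
| 0.95 | 0.95 | 25 | 0.5 |

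For AEs the comparison by response level is therefore very imprecise, in addition to being non-causal.

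**4. Referral follow-up.** No definition is given. The study process described runs from a text, to a nurse exchange, to a request to attend, which is 2wT only. A two-arm version (attending after suspecting an AE) is conceivable. A kept referral is, however, itself an in-person visit and an occasion on which an AE is found, so it overlaps both outcomes.

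**5. Urban/rural.** With no rural men the interaction cannot be estimated. Otherwise, with an assumed rural share s, take the control risk as 0.5% and the average risk difference as 1.5 points. The test is two-sided 5% with a normal approximation. Expected rural events use 497·s × 0.005 and 497·s × 0.02.

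| s (assumed) | rural AEs, control / 2wT | power if whole effect is urban | power if rural effect is half the average |
|---|---|---|---|
| 10% | 0.25 / 0.99 | 18% | 7% |
| 25% | 0.62 / 2.5 | 35% | 11% |
| 50% | 1.2 / 5.0 | 57% | 19% |

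Example, s = 25% with the whole effect urban: the urban difference is 0.015/0.75 = 0.02. SE = √[(2×0.005×0.995)/124.25 + (0.005×0.995 + 0.025×0.975)/372.75] = 0.0126. Then 0.02/0.0126 = 1.59, and Φ(1.59 − 1.96) ≈ 35%. With so few events these powers are only indicative.

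The two later phases in Table 2 are rural but opt-in, without a randomized control, so they cannot show whether setting modifies the arm effect.

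**The case against.** The strongest reply is that this is one loosely worded exploratory sentence, absent from the protocol's data analysis section, and that a description within the 2wT arm already fits it. That is fair as to importance, and it means that coding controls as zero is not the only way to proceed. But the SAP names response rate as a mediator and cites a moderator–mediator paper, so a conventional analysis is the natural reading and should be ruled out in writing.

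Three stronger readings are tempting, and the documents do not support them.

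- *Both mediators exist only in the texting arm.* This is clear for text response. Referral follow-up is undefined, both arms hold referral cards, and control men may seek unscheduled care. The SAP also uses response for both arms, though in the missing-data sense.
- *Collinearity makes the effects inseparable.* With M = A × R the variance inflation factor is 1 + mean²/(2·SD²). An assumed mean of 85% and SD of 20% gives 1 + 0.7225/0.08 = 10.0, but 50% and 30% gives 1 + 0.25/0.18 = 2.4. Neither pair is in the documents. Even in the first case the slope on visits has a standard error of about 1/(0.20 × √497) = 0.22 outcome SDs per unit of response, which is imprecise but estimable. The obstacle is non-randomized response, which the inflation factor does not measure.
- *Urban/rural has only one level.* Table 2 says otherwise for the randomized phase. This is a contradiction to resolve, and it does not prove that the moderator lacks variation. Nor does the shortage of AEs limit a visit-count analysis on about 994 men.

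**Conclusion.** The point holds for text response rate. It has no control-arm value, so a conventional mediation analysis through it cannot validly split the between-arm effect. This follows from the design and needs no assumed figures. For referral follow-up the finding is narrower: the term is undefined, and the only study pathway described is text-triggered. For the moderator, the protocol contradicts itself on setting. Whichever statement is right, about 12 expected AEs (on the SAP's assumed rates) cannot support an informative interaction on AEs.

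A reader might infer that neither analysis could ever yield anything valid. That goes too far: a description within the 2wT arm is possible, and setting can be examined for visits if both settings enroll. The noninferiority test, the main visit comparison and the sample size are untouched.

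**What to change.** 1. Remove text response rate as a mediator of the arm effect. In its place, describe visits and AE detection by response level within the 2wT arm, labelled exploratory and non-causal. Define response level and its denominator; the protocol text and Table 2 differ by one day on the texting period (days 1–14 v 1–13) and must be reconciled.
2. Treat referral follow-up in the same way unless it is defined and measured identically in both arms.
3. Reconcile protocol section 5, Future Plans, Table 2 and the SAP on the setting of the randomized trial. Keep urban/rural as a moderator only if both settings are enrolled, and say how a site is classed. If not, use site or district.
4. Limit the moderator analysis to visit count.

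The cost is wording in the SAP and in whichever protocol passage proves wrong, plus the loss of a mechanism claim that the trial could not have supported. No new data, and no change to sample size or primary analysis, are needed.

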#### 10. DATA ANALYSIS:

For Objective 1, the 2wT safety outcome of interest is cumulative AE rate (moderate or severe) ≤ Day 14. In RSA, and similar to other countries in the region. moderate AEs are those which include symptoms requiring modification of activity, but not resulting in loss of work or cancellation of social activities while severe AEs are those with incapacitating symptoms, requiring bed rest and loss of work 66. Incidence of AEs before Day 14 will be extracted from routine VMMC data for both 2wT and control. Incident AEs on Day 14 will be identified, classified, and graded for severity using routine NDOH protocols  and recorded on routine VMMC AE forms. We will compare cumulative rates of any moderate or severe AE ≤ Day 14 between groups using Fisher's exact test as the expected number of AEs is low. The rates will be calculated per arm as: (# moderate + severe AEs)/ (total # VMMC clients who attend/responded to 2, 7 or 14 Day follow-up visits or texts). Multivariate logistic regression models (any AE v none) will quantify the magnitude of difference, adjusting for any potential confounders. To determine follow-up visit reduction, we will compare the mean number of in-person visits for intervention and control using a t-test. A multivariate linear regression model will further quantify the effect of intervention on visit reduction, adjusting for potential confounders. Secondary outcomes include: AE rates on Day 14, texting response rate, time between 2wT AE text reporting and follow-up, severity of AEs. We will perform appropriate summaries of missing data and LTFU, testing for systematic differences in response by study arm. We hypothesize that 1) 2wT is non-inferior to routine follow-up for patient safety and that 2) 2wT will reduce unnecessary follow-up over standard care.

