**Expanding and Scaling Two-way Texting to Reduce Unnecessary Follow-Up and
Improve Adverse Event Identification Among Voluntary Medical Male
Circumcision Clients in the Republic of South Africa**

NCT04327271

[name], Principal Investigator

Statistical Analysis Plan (PDF/A) Version Date 8/26/19

Sample size and power:

RCT to determine no inferior AE ascertainment using 2-way texting rather than routine care. Randomization will be 1:1 between routine care and the texting intervention. If routine care AE ascertainment is 0.5% as evidenced from Aurum Institute program records, and 2-way texting increases AE ascertainment to 2.0% similar to our intervention arm AE ascertainment rate for the same intervention in our prior study in Zimbabwe (1.88%), and if we take -0.25% to be our noninferiority margin, and assume 10% LTFU, enrolling 1,104 men will give 80% power to establish noninferiority. In other words, 1,104 men (at least 994 of whom provide analyzable data) will provide at least 80% power to rule out a decrease of more than 0.25% based on the lower bound of the one-sided 95% confidence interval for the difference between arms in the proportion with AEs ascertained.

Sample sizes required to establish noninferior AE ascertainment using 2-way texting.

AE ascertainment		Sample size required for 80% power*		
Routine Care	2wText	N/group	Total N	+ 10% increase for LTFU
0.5%	1.50%	782	1564	1738
0.5%	2.00%	497	994	1104

* Calculated using Statistical Solutions Nquery Advisor version 8.4.1.0, two-group test of non-inferiority in proportions.

DATA ANALYSIS:

1. For the 2wT safety outcome of interest is cumulative AE rate (moderate or severe) \leq Day 14. In RSA, and similar to other countries in the region, moderate AEs are those which include symptoms requiring modification of activity, but not resulting in loss of work or cancellation of social activities while severe AEs are those with incapacitating symptoms, requiring bed rest and loss of work ¹. Incidence of AEs before Day 14 will be extracted from routine VMMC data for both 2wT and control. Incident AEs on Day 14 will be identified, classified, and graded for severity using routine NDOH protocols ² and recorded on routine VMMC AE forms.

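### The SAP's primary test can show that AE ascertainment is no worse with 2wT, but hypothesis 1 claims non-inferior patient safety and no visible criterion withholds that claim because of excess AEs

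*SAP*

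**What the plan says.** The SAP's sample-size section gives the purpose as an "RCT to determine no inferior AE ascertainment using 2-way texting rather than routine care". It assumes 0.5% ascertainment in routine care and 2.0% with 2wT, and the trial is powered "to rule out a decrease of more than 0.25% based on the lower bound" of the one-sided 95% interval.

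SAP Data Analysis item 1 applies the same rule, "by comparing the lower limit of the one-sided 95% confidence interval of the difference in proportion between groups, to the noninferiority margin". If AEs rise, "we will then seek to establish superiority of the two-way texting group by comparing arms with Fisher's exact test".

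The same item labels cumulative moderate or severe AEs to Day 14 as the safety outcome, and ends with the hypothesis that "2wT is non-inferior to routine follow-up for patient safety". Protocol section 10 uses the same label and the same hypothesis, and compares the arms "between groups using Fisher's exact test as the expected number of AEs is low", followed by a logistic model. Protocol section 4, Objective 1, also calls the AE rate a safety outcome and asks whether texting can safely reduce visits.

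**The concern.** The rule and the hypothesis answer different questions. The rule asks whether 2wT finds fewer AEs, so a higher AE proportion in the texting arm counts in its favour. The hypothesis asks whether patients are as safe, and for that question a higher AE proportion would ordinarily be a warning. The observed proportion mixes how often AEs occur with how often they are found, and the lower limit cannot separate the two.

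At stake is the wording of the main conclusion. The more AEs are recorded with 2wT, the more likely the test is to pass, and under the SAP that pass could be reported as non-inferior patient safety. This is the expected result, because the SAP plans for a fourfold rise in recorded AEs. Protocol section 12 says the findings will be used by the NDOH to inform follow-up visit schedules.

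**Working it through.** **Inputs (SAP, Sample size and power).** Control 0.5%; 2wT 2.0%; margin -0.25 points; one-sided alpha 0.05; power 80%; 1:1 allocation; 994 analysable, so 497 per arm. The SAP names no interval method, so I used the normal approximation and exact enumeration with Wald and Newcombe limits.

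**1. Reproduce the sample size.** With higher ascertainment as the favourable direction:

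n = (1.6449 + 0.8416)² × (0.005×0.995 + 0.02×0.98) / (0.015 + 0.0025)² = 6.1827 × 0.024575 / 0.00030625 = 496.1, rounded up to 497 per arm.

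The total is 994, and 994/0.9 = 1,104.4, against the SAP's 1,104. The distance of 1.75 points (1.5 + 0.25) arises only if more AEs is favourable. If an increase counted against 2wT with a 0.25-point margin, the planned +1.5 points would lie outside the margin and no sample size would give 80% power. The figures therefore confirm the direction of the test.

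**2. Chance that the test passes.** For a true 2wT proportion p, with SE = √[0.005×0.995/497 + p(1-p)/497]:

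P(pass) = Φ[(p - 0.005 + 0.0025)/SE - 1.645]

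- p = 0.5%: SE 0.447 points; 0.25/0.447 - 1.645 = -1.086; P = 0.139
- p = 2%: SE 0.703 points; 1.75/0.703 - 1.645 = 0.844; P = 0.801
- p = 3%: SE 0.828 points; 2.75/0.828 - 1.645 = 1.676; P = 0.953

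| True 2wT (control 0.5%) | Normal | Exact Wald | Exact Newcombe |
|---|---|---|---|
| 0.5% | 0.139 | 0.146 | 0.120 |
| 1% | 0.392 | 0.391 | 0.366 |
| 2% | 0.801 | 0.838 | 0.818 |
| 3% | 0.953 | 0.974 | 0.972 |

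**3. Single results at 497 per arm (control vs 2wT; one-sided 95% limits in points).**

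| AEs | Wald | Newcombe | Outcome under the SAP |
|---|---|---|---|
| 3 vs 3 | -0.81, +0.81 | -0.97, +0.97 | fails |
| 3 vs 8 | -0.08, +2.10 | -0.13, +2.28 | passes |
| 3 vs 12 | +0.54, +3.08 | +0.54, +3.27 | passes; Fisher p = 0.034, read as superiority of 2wT |

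Equal counts fail, and an excess of five AEs passes.

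**4. Expected upper limit in the planning case (Wald).** 1.5 + 1.645 × 0.703 = +2.66 points.

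**5. Could the Fisher test serve as the safety check?** Exact two-sided p < 0.05 with 2wT higher, at 497 per arm, occurs in 7% of trials for a true doubling (0.5% vs 1%), 24% for a tripling and 47% at 0.5% vs 2% (the SAP states 45%). A non-significant result does not exclude an excess, and the SAP reads a significant increase in favour of 2wT.

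**The case against.** Four arguments on the other side deserve weight.

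- **Ascertainment bears on safety.** Surgery is routine and outside the study, and men with an intraoperative AE are ineligible (protocol section 5). What changes is follow-up, so missed or late AEs are a central risk. The SAP's title, purpose, margin and table heading all speak of identifying or ascertaining AEs, and the protocol's Future Plans speaks of detection. This stands: the test is reasonable for ascertainment, and ruling out under-detection is a relevant part of safety. It does not turn a lower limit into a limit on harm.
- **The design gives other information.** Both arms are asked to attend an in-person Day 14 review, which helps to separate detection from incidence. Severity, Day 14 AE rates and time from text to follow-up are secondary outcomes. The protocol's logistic model would give an estimate informative in both directions. These help interpretation, but none carries a bound or decision rule, and the Day 14 reviewers are unmasked routine providers.
- **A reader might infer that nothing could withhold a safety claim.** The documents do not support that. The lower-limit test withholds it when too few AEs are found, and with both arms at 0.5% it fails in about 85-88% of trials. What is missing is a criterion that responds to too many AEs.
- **Some text is not visible.** No text is visible under the sample-size heading in protocol section 9, and the DSMB charter is listed as an appendix that is not included. Either might hold a limit on excess AEs. The DSMB's power to stop the study is trial oversight and does not define the final claim.

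**Conclusion.** The mismatch is real and internal to the SAP, and the protocol shares its hypothesis wording. A pass supports a statement that AE ascertainment is not lower with 2wT by more than 0.25 points. It does not support a statement that AEs are no more frequent. At 497 per arm with control at 0.5%, the chance of a pass rises from 12-15% at equal proportions to 80-84% at 2% and 95-97% at 3%. A passing result can be compatible with an excess above 2 points.

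These figures assume the SAP's control proportion and analysable number, and the ranges cover the unnamed interval method. That no criterion responds to an excess is a statement about the visible text only.

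It would go too far to infer that 2wT is expected to cause harm, since the planned rise may be entirely better detection. It would also go too far to say that the test has no bearing on safety. This should be fixed: the test and sample size can stay as they are, but the claim attached to them is wider than they support.

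**What to change.** 1. **Reword the claim.** In SAP Data Analysis item 1 and protocol section 10, name the endpoint AE ascertainment and restate hypothesis 1 as: *AE ascertainment with 2wT is non-inferior to routine follow-up.* Call the Fisher step a test for higher AE ascertainment. Add: *A pass shows no worse detection of AEs; it does not exclude more AEs with 2wT.* Bring the safety-outcome label in protocol section 4 into line. The word safely in Objective 1 may stay if it is qualified in the same way.
2. **Report the other side of the interval.** Give the two-sided 90% interval of the arm difference for moderate-or-severe AEs and for severe AEs alone, as descriptive safety information read alongside the Day 14 findings. State that the first mixes detection with harm and that the second will be imprecise: with 0 of 497 severe AEs in an arm, the one-sided 95% upper limit for that arm is 1 - 0.05^(1/497) = 0.60%.
3. **Only if a formal safety claim is wanted:** add a separate upper-limit test with a margin that the sponsor justifies. The visible text gives none, and this review proposes none.

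Items 1 and 2 cost wording and two intervals from data already collected. Randomisation, data collection and sample size do not change. The downside is a narrower headline claim.
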